6.2 Determination of sample size

To determine the required sample size, we run a series of simulation using the software R. Assuming a mean number of six staff members (range two to nine) per health facility and a mean number of five times a person was supposed to wash their hands ($SD=5$) and an intra cluster correlation coefficient of 0.15, we need to enrol 10 health facilities in each trial arm to detect difference of 15%-points in the proportion of handwashing during the five critical moments of the WHO (30% control versus 45% intervention) with 81% power at a two-sided 5% significance level. To account for potential loss to follow-up we aim to enrol in total 24 health facilities.

For Modules 1 and 3, all HCWs who are present during data collection and eligible will be asked to participate in the study. For Module 2, the observations a maximum of 10 HCWs per PHCF will be followed in order to avoid disturbing the daily routines of the PHCF too much. Module 4 follows the sample size calculation of the cRCT design, hence 24 PHCFs will be monitored. For Module 5, 6-10 FGDs will be administered and for Module 6, 10-20 interviews.

6.3 Description of statistical methods

Baseline characteristics will be summarized using descriptive statistics. The difference in the observed proportion of always handwashing in the five critical moments as defined by WHO between two study arms at follow-up will be investigated using mixed effect logistic regression models with random intercepts for health care facilities. In the primary analysis only the intervention will be included as predictor.

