Objective(s)	
Primary objective: Evaluate the effects of the comprehensive h4h handwashing intervention on hand hygiene in PHCFs in Mali and Burkina Faso.
 
Secondary objectives:
 
 1) Assess hygiene-related risks, attitudes, norms, abilities and self-regulation (RANAS) behavioural factors of health care providers 2) Assess the impact of the h4h intervention package on hygiene-related RANAS behavioural factors of health care providers 3) Explore perceived effects on health and wellbeing of the hands4health intervention package in PHCFs
Primary Endpoint Secondary Endpoints	
The primary endpoint of this study will be good handwashing practice defined as health care workers (HCWs) who wash their hands with water and soap almost always in the five critical moments of the World Health Organization assessed by structured handwashing observations. Critical moments are:
 
 i) Before touching a patient ii) Before clean/aseptic procedures iii) After risk/exposure to body fluids iv) After touching a patient v) After touching a patient’s surroundings 
The secondary endpoints in the survey are:
 
 A) Self reported handwashing practice answered for each critical moment on a Likert scale ranging from almost never to almost always.

	
B) Number of total coliforms and E.coli colony-forming units (CFUs) per hand before handwashing.
 
C) Hygiene-related health outcomes which are summarized in table 3. The health outcomes will be reassessed with local experts of the respective countries to assure feasibility before the start of the intervention.

Study Design
	
Overall project: Multi-center cluster-randomized controlled trial (cRCT) design.
 
Module 1-3 will be repeated three times within the cRCT at baseline, two months post-intervention and at endline. Module 4 data collection will take place in both study arms longitudinally starting after the intervention has been implemented. Module 5 and 6 are qualitative focus group discussions (FGDs) and interviews and will take place after the second round of data collection in Modules 1-3. For Module 2, only a maximum of 10 HCWs per facility will be observed.

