4.1 Primary endpoint

The primary endpoint is the number of times a participant performs good handwashing practice with soap at critical moments assessed by structured handwashing observations over half an hour to an hour per HCW. The number of critical moments serves as denominator. Critical moments are defined by the WHO as:

- i) Before touching a patient
- ii) Before clean/aseptic procedures
- iii) After risk/exposure to body fluids
- iv) After touching a patient
- v) After touching a patient's surroundings

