6.3.1.1 Primary Analysis

Module 1: Combined RANAS and KAP survey: The data will be summarized using descriptive statistics. Associations of RANAS behavioural factors with good handwashing practices and health care worker's characteristics with the other outcome variables from RANAS behavioural factors will be estimated using random effect linear regression modelling and random effect logistic regression modelling. Missing data will clearly be reported but not imputed.

Module 2: Structured handwashing observations: To quantify the intervention effect logistic regression with binomial distribution with random intercepts for health care facilities models will be applied.

Module 3: Microbiological analysis of hand rinse samples: For investigating factors associated to *E.coli* and total coliform prevalence on HCWs hands, random effect linear regression models will be applied.

Module 4: Diary approach for pre-defined health outcomes: . The sum of each outcome variable separately per facility will be used as a measure for statistical analysis. To quantify the intervention effect on hygiene-related health outcomes, random effect linear regression modelling will be used.

Modules 5 and 6, FGDs and KIIs: FGDs and KIIs will be audio recorded, transcribed, and translated if necessary for further analysis. The local perception of the success and sustainability of the h4h intervention will be analysed using the framework method with the software MaxQDA (VERBI Software, Marburg, Germany) or NVivo (QSR International, Melbourne, Australia) (48).

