6.3.1.2 Secondary Analyses

In a secondary analysis the models will be adjusted for known confounder and additional predictors imbalanced at baseline.

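### If observed handwashing is analysed per critical moment, the models need a worker-level random intercept: a small gain for the arm effect, a large one for worker-level covariates

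*Combined protocol and SAP*

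**What the plan says.** Section 6.3 specifies "mixed effect logistic regression models with random intercepts for health care facilities". For Module 2, section 6.3.1.1 repeats the structure: "logistic regression with binomial distribution with random intercepts for health care facilities models will be applied". Neither section, nor any other, adds a worker-level random effect, a robust variance or an overdispersion term to the handwashing model. On fixed effects, section 6.3 says: "In the primary analysis only the intervention will be included as predictor". Section 6.3.1.2 then says: "In a secondary analysis the models will be adjusted for known confounder and additional predictors imbalanced at baseline".

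The documents do not agree on the unit of analysis:

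- Section 4.1 counts handwashes per participant and says: "The number of critical moments serves as denominator".
- Section 6.2 sizes the trial on "a mean number of five times a person was supposed to wash their hands", with an SD of 5.
- The synopsis instead defines the endpoint as "health care workers (HCWs) who wash their hands with water and soap almost always in the five critical moments", and section 6.3 also words the outcome as always washing. On that reading each HCW gives one result per round.

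**The concern.** On the per-moment reading the data have three levels: moments within HCWs within facilities. The planned model has two. It correlates all moments in a facility equally and makes no allowance for the moments of one HCW being more alike than those of two colleagues. With a mean of 5 and an SD of 5, some HCWs supply many moments and others very few, so a busy HCW can dominate a facility's total.

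Two things are at stake. The first is the efficiency of the arm comparison and, in some settings, its error rate. The second is inference on factors that vary between HCWs in the same facility. Section 4.2 lists age, education, sex, previous training and position as covariates, with good handwashing practice as the outcome. Table 2 assigns logistic regression of Module 2 data to the first secondary objective. A facility intercept does not protect the standard errors of such factors.

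**Working it through.** **Inputs.** From section 6.2: "Assuming a mean number of six staff members (range two to nine) per health facility"; moments per HCW with mean 5 and SD 5; ICC 0.15; 30% versus 45%; 10 facilities per arm for 81% power; 24 facilities enrolled (12 per arm). The synopsis gives 24 per country, 48 in total (24 per arm). Section 6.2 does not state the level or scale of the ICC. The documents give no worker-level variance, so it is assumed and varied.

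**The plan's own figure.** 6 × 5 = 30 moments per facility, so 300 per arm with 10 facilities.

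- Facility ICC of 0.15: design effect 1 + 29 × 0.15 = 5.35, effective sample 300/5.35 = 56 per arm, power about 37%. Simulating the planned model gives 42-50%.
- Worker-level ICC of 0.15: design effect 1 + 4 × 0.15 = 1.6 with equal moments (85%), or 1 + 9 × 0.15 = 2.35 with SD 5 (70%). Simulation gives 71-77%.

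The 81% is not reproduced on either reading. This matters here only because it leaves open whether facilities are assumed to differ.

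**Arm effect.** A facility ICC of 0.15 on the latent scale is a logit variance of (0.15/0.85) × π²/3 = 0.58. Data sets were simulated with 12 facilities per arm, and the planned model and a nested model (HCW within facility added) were fitted to each. Tests are Wald with a normal reference. Error rates use 2,000-3,000 runs and power uses 1,500.

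| Worker variance | False positives, facility only | False positives, nested | Power, facility only | Power, nested |
|---|---|---|---|---|
| 0 | 7.5% | 7.5% | 54.4% | 54.5% |
| 0.5 | 6.6% | 6.8% | 53.1% | 54.7% |
| 1 | 7.2% | 7.1% | 52.5% | 53.9% |
| 2 | 7.3% | 7.1% | 51.2% | 53.9% |

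Monte Carlo error is about 0.5 points for error rates and 1.3 for power. The largest power gap is 47.2% versus 51.3%, by likelihood-ratio test at worker variance 2. With 24 per arm and worker variance 1, false positives are 5.9% versus 5.3% and power is 75.6% versus 77.5%. With 10 per arm, false positives are 8.3% versus 7.3%.

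The excess over 5% is present with no worker variance and in the nested model too. It comes mainly from the normal reference with few clusters. With a t reference on 24 − 2 = 22 degrees of freedom, the facility-only model gives 5.4-6.0% and the nested model 5.2-6.1%.

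The picture changes when facilities hardly differ (facility-only versus nested, Wald, 12 per arm):

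- Facility variance 0: 7.4% versus 4.9%, 7.2% versus 4.5% and 6.9% versus 5.9% at worker variance 0.5, 1 and 2.
- Facility variance 0.05, worker variance 1.5: 8.2% versus 5.3% in 1,250 runs; a separate check gave 7.8% versus 4.6%.

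**HCW-level covariate with no true effect, facility-only model.** Two sets of simulations were run: set A with 500 runs per setting, set B with 1,500 runs and facility variance 0.58.

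| Worker variance | Rejection, set A | Rejection, set B |
|---|---|---|
| 0.5 | 14.4% | 12.4% |
| 1.0 | 19.2% | 18.8% |
| 1.5 | 22.4% | 21.9% (facility variance 0.05) |
| 2.0 | not run | 24.3% |
| 2.5 | 26.6% | not run |

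Standard errors were 24-44% too small in set A and 22-41% in set B. Adding the HCW intercept brought rejection down to 6-8% (600 runs per setting). A separate check gave 18-23% without the HCW intercept and 4-7% with it.

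A hand check at worker variance 1 uses p = 0.30. The within-worker correlation on the proportion scale is about 0.21 × 1/(1 + 0.21 × 1) = 0.17. The moment-weighted number per HCW is 5 + 25/5 = 10. The design effect is 1 + 9 × 0.17 = 2.5, so the standard error is too small by a factor of 1/√2.5 = 0.63. The rejection rate is then 2 × [1 − Φ(1.96 × 0.63)], about 22%. That is close to the simulated 19%.

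**The case against.** The strongest case against has four parts.

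- **The primary test is protected.** Treatment is assigned by facility, and the facility intercept absorbs the worker variation that reaches the facility mean. This stands. A reader might infer that repeated moments simply count as independent and that the main test is badly inflated. The documents do not support that: moments are independent only given the facility. A model with no random effect at all rejects 35-39% of true nulls at facility variance 0.58, against about 7% for the planned model.
- **A worker term would not cure the excess over 5%.** This also stands at a facility ICC of 0.15, and it is why a small-sample reference belongs in the remedy.
- **The covariate error rates answer a different question.** Section 6.3.1.2 adjusts in order to estimate the intervention effect and announces no test of the covariates. The association models under Module 1 in section 6.3.1.1 say only that random effects are used, without naming the level. It would therefore be wrong to say that the plan commits to facility-only tests of HCW factors. But Table 2 does foresee regressions on Module 2 data, and the only structure named for observed handwashing is facility-only.
- **The unit may be the HCW.** On the synopsis wording there is one result per HCW per round and the point falls away. Sections 4.1 and 6.2 and the binomial model point to moments, so the plan has to say which it means.

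**Conclusion.** The point holds as a cheap improvement, with moderate confidence, on condition that observed handwashing is analysed per moment.

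For the arm effect, omitting the worker level costs about 0-4 points of power. It raises the false-positive rate to about 7-8%, from about 5%, only when between-facility variance is near zero. At a facility ICC of 0.15 the rate is essentially the same with or without the worker term. The near-zero case cannot be excluded, because section 6.2 does not say whether 0.15 describes facilities or workers.

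For HCW-level covariates in any facility-only model of observed handwashing, standard errors are about 20-40% too small and a true null is rejected about 12-27% of the time. These sizes rest on assumed worker variances of 0.5 to 2.5. A reader should not carry them over to the primary comparison.

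**What to change.** - **Unit.** In sections 6.3 and 6.3.1.1 (Module 2), state that the outcome is washes out of moments observed per HCW, and reconcile the synopsis and section 6.3 with section 4.1.
- **Model.** Fit random intercepts for the facility and for the HCW within facility, in the primary model, the adjusted models and any model relating HCW factors to observed handwashing. Fall back to the facility intercept alone if the worker variance is estimated at zero.
- **Reference distribution.** Test the arm effect with a small-sample reference, for example t with facilities minus 2 degrees of freedom.
- **ICC.** State the level and scale of the 0.15 in section 6.2.

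The cost is a few sentences and one variance term. The unique ID that links survey and observations (section 4, Module 2, and section 9.4) already identifies the HCW. The downsides are occasional convergence trouble and the price of an honest reference: at 12 facilities per arm and worker variance 1, nested-model power falls from 53.9% (normal reference) to 49.9% (t).

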6.3.1 Datasets to be analysed, analysis populations

For the primary analysis we will use the available case population of HCWs which will be analysed according to the intention-to-treat principles.

6.3.1.1 Primary Analysis

Module 1: Combined RANAS and KAP survey: The data will be summarized using descriptive statistics. Associations of RANAS behavioural factors with good handwashing practices and health care worker's characteristics with the other outcome variables from RANAS behavioural factors will be estimated using random effect linear regression modelling and random effect logistic regression modelling. Missing data will clearly be reported but not imputed.

Module 2: Structured handwashing observations: To quantify the intervention effect logistic regression with binomial distribution with random intercepts for health care facilities models will be applied.

Module 3: Microbiological analysis of hand rinse samples: For investigating factors associated to *E.coli* and total coliform prevalence on HCWs hands, random effect linear regression models will be applied.

Module 4: Diary approach for pre-defined health outcomes: . The sum of each outcome variable separately per facility will be used as a measure for statistical analysis. To quantify the intervention effect on hygiene-related health outcomes, random effect linear regression modelling will be used.

Modules 5 and 6, FGDs and KIIs: FGDs and KIIs will be audio recorded, transcribed, and translated if necessary for further analysis. The local perception of the success and sustainability of the h4h intervention will be analysed using the framework method with the software MaxQDA (VERBI Software, Marburg, Germany) or NVivo (QSR International, Melbourne, Australia) (48).

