Module 1: Combined RANAS and KAP survey	SO1: Hygiene-related RANAS behavioural factors of HCWs at baseline	- Descriptive statistics, multiple linear and logistic regression models
Module 2: Structured handwashing observations	SO1: Hygiene-related RANAS behavioural factors of HCWs at baseline SO2: Impact of h4h intervention on hygiene-related RANAS behavioural factors of HCWs	- Descriptive statistics, multiple linear regression models and logistic regression models
Module 3: Microbiological analysis of hand rinse samples	SO1: Hygiene-related RANAS behavioural factors of HCWs at baseline SO2: Impact of h4h intervention on hygiene-related RANAS behavioural factors of HCWs	- Analysis of E. coli and total coliforms - Descriptive statistics, multiple linear regression models
Module 4: Diary approach for pre-defined health outcomes	EO1: Effects of h4h intervention package on health outcomes and absenteeism	- Descriptive statistics
Module 5: Focus Group Discussions	SO3: Perceived effects of the h4h intervention package	- Framework methodology
Module 6: Key informant interviews	SO3: Perceived effects of the h4h intervention package	- Framework methodology

The Swiss TPH assessed the health care worker's understanding of hygiene and expected positive and negative impacts of the intervention with Gravit'eau with focus group discussions (FGDs) in 18 facilities in Mali and 9 facilities in Burkina Faso (more facilities are still being investigated). Local collaborators from Tdh and the regional ministries of health were involved from the study's kick-off meeting onwards and are regularly being consulted in bi-weekly meetings and additional ToC workshops led by Skat Foundation. The data collection methods for each module will be described in further detail:

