The Whirl-Pak bags containing the samples will be kept on ice in an isolation box and processed within 4 hours of sampling (45). Membrane filtration will be used to detect colony-forming units (CFUs) of *E. Coli* and total coliforms. In a field laboratory, the content of the bags will be passed through a 47-mm-diameter 0.45 µm cellulose filter. The filter paper will then be placed on growth media and incubated at 35°C ± 0.5°C for a duration of 24 hours for *E. Coli* and total coliforms (45). We plan to filter 100 mL per bag to detect CFUs of *E. Coli* and total coliforms. The exact amount of mL will be established during piloting as the volume used is dependent on the degree of bacterial contamination on the hands. Compact dry plates will be used for the detection of *E. coli* and total coliforms.

The lower detection limit of CFUs will be calculated by dividing 1 CFU/plate by the filtrate volume and then multiplying it with the total Whirl-Pak volume of 350 mL. The upper detection limit will be calculated by dividing 500 CFUs/plate by the filtrate volume and then multiplying it with the Whirl-Pak volume. For the statistical analysis, the CFUs per hand will be normalized and \log_{10} transformed (45).

Module 4: Diary approach for pre-defined health outcomes: Longitudinal data on hygiene-related health outcomes of patients and disease-related absences of HCWs will be collected during

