4.2 Secondary endpoints

The most important secondary endpoints in the survey are:

- A) Self reported handwashing practice to answer for each critical moment on a Likert scale ranging from almost never to almost always.
- B) The log-transformed number of total coliforms and E.coli CFUs per hand before handwashing.
- C) Hygiene-related health outcomes which are summarized in table 3. The sum of each outcome variable separately per facility will be used as a measure for statistical analysis. The health outcomes will be reassessed with local experts of the respective countries to assure feasibility before the start of the intervention.

Table 3: Hygiene-related health outcome variables for Module 4.

Outcome variable	Details
Absenteeism of health care worker	
 • Record of the event • Number of days absent • Reason for absence
Maternal mortality	
 • Record of the event • If known, reason of passing
Neonatal mortality	
 • Record of the event • If known, reason of passing
Neonatal sepsis(49)	
 • Record of the event • Number of days treated • Outcome (healthy, unknown, death)
Umbilical cord infection	
 • Record of the event • Number of days treated • Type of infection • Outcome (healthy, unknown, death)
Wound infection after stitching of surgical procedures	
 • Record of the event • Number of days treated • Outcome

Covariates were assessed with a directed acyclic graph (DAG) with RANAS variables as exposure variables and good handwashing practice as outcome variable (Appendix). Covariates for estimating the total effect of RANAS on good handwashing practice are age, education, sex, socio-economic status, previous training in hygiene, handwashing practices, position in the health care facility, and the water infrastructure of the health care facilities.

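### For secondary endpoint B (log10 CFU per hand), the Module 3 analysis text names no arm comparison and calls the outcome prevalence

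*Combined protocol and SAP*

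**What the plan says.** The endpoint is named in four places in the combined protocol and SAP.

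- Synopsis, secondary endpoint B: "Number of total coliforms and E.coli colony-forming units (CFUs) per hand before handwashing".
- Section 4.2, endpoint B, listed among the most important secondary endpoints: "The log-transformed number of total coliforms and E.coli CFUs per hand before handwashing".
- Section 4, Module 3 methods: "For the statistical analysis, the CFUs per hand will be normalized", followed by a log10 transformation.
- Section 6.3.1.1, Module 3: the paragraph opens "For investigating factors associated to" and, after naming E. coli, continues "total coliform prevalence on HCWs hands, random effect linear regression models will be applied".

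The neighbouring paragraphs of 6.3.1.1 state a different kind of aim. Module 2: "To quantify the intervention effect logistic regression with binomial distribution with random intercepts for health care facilities models will be applied". Module 4: "To quantify the intervention effect on hygiene-related health outcomes, random effect linear regression modelling will be used".

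Table 2 in section 4 assigns Module 3 to two objectives, one of which is "SO2: Impact of h4h intervention on hygiene-related RANAS behavioural factors of HCWs". For Module 3 it lists descriptive statistics and multiple linear regression.

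**The concern.** An analyst who works from 6.3.1.1 finds an outcome word that does not match the endpoint definition, and an aim that does not include the trial's own question for that endpoint. A model of associated factors may or may not contain trial arm. If it does, arm is one predictor among several, and the follow-up round is not named.

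This matters more here than for a typical secondary endpoint. Section 4.3 says that participants, data collectors and the statistician cannot be blinded, but that the staff who count CFUs will be. The same section expects a Hawthorne effect in the handwashing observations and desirability bias in the survey. The hand-rinse count is therefore the endpoint best placed to corroborate the primary result, yet the analysis section does not say how its treatment effect will be estimated. If this stays open, the round, the organism and the covariates of any reported CFU comparison can be settled after the data are seen.

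**Working it through.** The plan states no sample size or power for CFU. The 81% power in section 6.2 concerns observed handwashing. There is thus no figure to reproduce, and the check is mainly a comparison of texts.

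**Step 1: which scale is the outcome on?** Section 4.2 and the Module 3 methods agree on log-transformed CFU per hand. The synopsis names the measured quantity and is compatible with both. The Module 3 methods also give formulas for the detection limits. At the planned 100 mL filtered from 350 mL (a volume still to be confirmed in piloting):

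- lower limit = 1 / 100 × 350 = 3.5 CFU per hand, log10 = 0.54;
- upper limit = 500 / 100 × 350 = 1,750 CFU per hand, log10 = 3.24.

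These are limits for a quantified count. Section 6.3.1.1 then applies a linear model, which suits log10 CFU. Only the word prevalence is out of line.

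**Step 2: what is each model in 6.3.1.1 for?**

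| Module | Outcome named | Stated purpose |
|---|---|---|
| 2 | observed handwashing | intervention effect |
| 3 | E. coli and total coliform prevalence | associated factors |
| 4 | sums of health outcomes per facility | intervention effect |

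**Step 3: does another section supply the contrast for Module 3?**

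- Table 2 links Module 3 to the impact objective SO2, but SO2 is worded for RANAS factors, and the table gives no contrast and no round.
- Section 6.1.2 has hypotheses on RANAS variables and on health outcomes, none on CFU.
- Section 6.3 compares the arms at follow-up for observed handwashing only. Its sentence making the intervention the sole predictor follows directly on that model.
- Section 6.3.1.2 adjusts models for confounders and baseline imbalance, but defines no arm effect that 6.3.1.1 leaves out.

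None of them does.

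**Step 4: how much is left open?** Hands are sampled at baseline, two months after the intervention and at endline, so there are two post-intervention rounds. With two organisms this gives 2 × 2 = 4 possible arm comparisons. Allowing each to be unadjusted or adjusted gives 4 × 2 = 8.

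**Step 5: what does the baseline covariate cost?** With two arms, 24 facilities leave 24 − 2 = 22 cluster-level degrees of freedom, or 21 after a facility-level covariate. With the 48 facilities given in the synopsis, the figures are 46 and 45. Any term for country or randomisation stratum would come off these.

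**The case against.** The case on the other side is that the plan, read as a whole, already answers the question. The scale is fixed in two places. Section 6.3.1.1 uses logistic models where it means a binary outcome, and Table 2 lists both linear and logistic models for Modules 1 and 2 but only linear ones for Module 3. The module is measured in both arms before and after the intervention, with blinded counting, and is tied to an impact objective. The Module 3 paragraph also stands under the heading of the primary analysis, for which section 6.3 makes the intervention the only predictor.

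Most of this stands. It rules out one tempting inference, that the plan replaces the count by presence or absence and so discards information. No text defines a positive hand or a yes/no outcome, so any power loss from dichotomising would describe an analysis that the documents do not state. It also makes it likely that the authors mean to compare the arms.

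It does not close the gap. A model with the intervention as sole predictor cannot also be a search for associated factors, so the sentence in 6.3 does not fit the Module 3 paragraph. An intention inferred from Table 2 still lacks a contrast and a round.

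It is also fair to say that baseline adjustment is a choice made for precision, not the correction of an error, and that it departs from the arm-only model in 6.3.

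**Conclusion.** The point holds as a gap in specification. Section 6.3.1.1 does not state the arm effect on log10 CFU per hand or the round at which it is estimated, and its outcome word disagrees with section 4.2 and the Module 3 methods. Followed as written, it produces no treatment estimate for endpoint B.

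A reader might go further and infer that the trial will not compare arms on CFU at all. The link to SO2 and the two-arm sampling speak against that; what is missing is the specification.

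The consequence is four unadjusted candidate comparisons without a pre-stated choice, and no bias or power loss that can be put in figures. The conclusion rests on the text alone and needs no assumption about contamination levels. It concerns a secondary endpoint, so the change is advisable but does not touch the primary analysis.

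**What to change.** Rewrite the Module 3 paragraph of section 6.3.1.1 as follows.

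- Replace prevalence by log10 CFU per hand, for E. coli and total coliforms separately.
- State that a linear mixed model with a random intercept for facility estimates the difference between arms at the named post-intervention round or rounds.
- Adjust for the facility's mean log10 CFU at baseline, which is already collected. A facility mean can be used even when the workers present differ between rounds.
- Keep the model of associated factors as an additional analysis, labelled as such.

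While that paragraph is open, it would help to say how values outside the detection limits enter the log10 scale, since section 4 defines the limits but not their handling.

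The cost is some wording, one extra model (fitted once per organism) and one cluster-level degree of freedom. No new data are needed.
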